## 8 Study Subjects

### 8.1 Disposition of Subjects and Withdrawals

A summary by treatment group will be provided for the following:

- Number of randomized subjects,
- Number in Full Analysis Set (FAS);
- Number of subjects included in the Per Protocol Set & Reasons for Exclusion
- Number who died in ICU
- Number discharged from ICU
- Number who died in-hospital (after ICU)
- Number discharged from hospital
- Number with Day 180 assessment
- Number who died prior to Day 180 assessment
- Number lost to follow-up prior to Day 180 assessment

### 8.2 Protocol Violations and Deviations

Important protocol violations and deviations that can impact the results of the statistical analyses will be fully documented prior to database lock in the Analysis Sets Specification Document.

## 9 Demographics and Other Baseline Characteristics

All data recorded at baseline will be summarized by treatment group.

Because this was an open-label study, formal statistical comparisons between groups will be done using the methods described above in section 7.3.

Summaries will be presented for FAS and PPS separately.

The following baseline information will be presented:

- Demographic and clinical characteristics
- Medical history
- Prior chronic medications
- Cardiac arrest characteristics (including cause of arrest)
- Admission characteristics
- PCI
- Sofa score

## 10 Primary and Secondary Endpoints

### 10.1 Primary Endpoint

The primary endpoint will be summarised by randomised treatment group.

Since it is expected that a substantial proportion will have missing data for the primary endpoint (due to early mortality or other reasons), a statistical analysis that does not take account of this missingness is very likely to be subject to considerable bias.

Therefore, missing primary endpoint data will be imputed using the imputation model described in section 7.4.

In each imputation sample, the data will be analysed using an ANOVA that includes a factor for randomised treatment and the stratification factor of shockable rhythm. The results of the analyses will then be combined with standard methodology, using SAS PROC MIANALYZE.

The effect of randomised group will be estimated by the difference between groups and presented along with its associated 95% confidence interval.

The statistical analysis of the primary endpoint will be performed for the FAS and PPS.

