6.4. Baseline Characteristics to be collected

Baseline characteristics to be collected:

- Informed Consent
- Compliance with the inclusion/exclusion criteria will be documented
- Age
- Gender
- Medical history (chronic heart failure, previous AMI, previous cardiac surgery, previous arrhythmia, arterial hypertension, diabetes mellitus, COPD, chronic kidney disease, stroke)
- Chronic medication
- Arrest Characteristics (Public vs private place, bystander witnessed, bystander CPR performed, presenting rhythm, time to ROSC)
- Admission Characteristics (MAP, PaCO₂, PaO₂, Lactate, pupillary reflex, corneal reflex, FIO₂, dose of norepinephrine and dobutamine)
- Cause of arrest (STEMI, NSTEMI, arrhythmogenic, hypoxic, unknown)
- Angiography performed (time in hospital, time in cathlab, time in ICU)
- PCI performed
- SOFA score

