6.9.3. General statistics

All data will be managed by the LCC in conjunction with the Steering Committee. Data will be entered and reviewed on an ongoing basis. Key listings and tables will be defined by the Steering Committee. Tables, listings and raw data (as SAS transport files) will be made available to the members of the Steering Committee upon request.

The statistical analysis of the primary and all secondary efficacy endpoints will be performed in the modified Full Analysis Set (FAS), defined as all randomly assigned patients except those withdrawing informed consent for use of all trial data and in case many protocol violations are observed throughout the study, a Per Protocol Set (PPS) will be defined and all efficacy analyses will be repeated on the PPS.

All continuous data will be presented by treatment group using the number of non-missing observations, mean, standard deviation, median and (Q1,Q3). Categorical data will be presented by treatment group using the observed frequencies and percentages for each category.

The primary endpoint (% voxels with ADC < 0.650 mm²/s) will be analyzed by means of an analysis of variance (ANOVA) that includes randomized group and initial shockable rhythm as factors. The treatment effect will be estimated by the difference between treatment groups and presented along with its corresponding 95% confidence interval. Missing values for patients who die prior to the DW-MRI will be imputed on the basis of age, gender, presence of basic life support, presence of initial shockable rhythm, duration of advanced life support, neuron specific enolase, presence of a malign EEG pattern on day 1, final outcome at ICU discharge and allocated treatment arm.

Continuous and normally distributed secondary endpoints will be analyzed by means of an ANOVA including randomized treatment and initial shockable rhythm as factors in the model. Estimated treatment differences will be presented with their 95% confidence interval. Continuous secondary endpoints that show serious deviations from a normal distribution will be analyzed by means of a Van Elteren that includes the initial shockable rhythm as stratification factor. Binary secondary endpoints will be analyzed by means of a stratified Chi-squared test. Treatment differences will be expressed as risk ratios and presented along with their corresponding 95% confidence intervals.

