## 5 Sample Size Determination

Based on the results of a pilot study at Stanford University in which the standard deviation of the percentage  $ADC < 0.650 \text{ mm}^2/\text{s}$  in comparable post-CA patients was 8.9%, it was estimated that 56 patients would be necessary in each study group to show a 40% reduction in the extent of cerebral ischemia with a power of 80% at a two-sided alpha level of 0.05.

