#### **7.4 Methods for Withdrawals, Missing Data and Outliers**

For the primary endpoint, multiple imputation methodology will be used to account for missing data. A total of 100 imputations will be done. The imputation model will include the following:

Age, gender, presence of bystander CPR, presence of initial shockable rhythm, neuron specific enolase at days 1-2-3-4-5, presence of a malign EEG pattern on Day 1 and allocated treatment and death within 7 days of randomisation.

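### The primary ANOVA is valid but adjusts only for shockable rhythm; prespecified adjustment for age, time to ROSC and bystander CPR could gain precision at little cost

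*SAP*

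**What the plan says.** SAP 10.1 imputes missing primary-endpoint values and then states that "the data will be analysed using an ANOVA that includes a factor for randomised treatment and the stratification factor of shockable rhythm", with the results pooled across imputations. Protocol 6.9.3 likewise plans an "analysis of variance (ANOVA) that includes randomized group and initial shockable rhythm as factors". Neither document plans a covariate-adjusted primary or sensitivity analysis. The title of SAP 7.8 mentions covariates, but the section lists only exploratory subgroups and their interactions with treatment.

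The baseline data in protocol 6.4 include age and "Arrest Characteristics (Public vs private place, bystander witnessed, bystander CPR performed, presenting rhythm, time to ROSC". The plan uses these variables in other places:

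- The SAP 7.4 imputation model contains "Age, gender, presence of bystander CPR, presence of initial shockable rhythm", followed by post-randomisation items (NSE on days 1 to 5, the day-1 EEG, early death) and treatment arm. Time to ROSC is not in it.
- SAP 10.2.3 reuses the 7.4 list as baseline covariates in a survival model.
- SAP 7.8 uses age, time to ROSC and bystander CPR as subgroup factors for the primary endpoint.

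None of the three enters the model that estimates the treatment effect.

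**The concern.** In a randomised comparison of a continuous outcome, a baseline variable that predicts the outcome but is left out of the model adds to the residual variance. A chance imbalance in it between arms also passes into the estimate. Adjusting for a prespecified set of baseline variables shrinks the residual variance and leaves the type I error rate intact.

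What is at stake is precision on the one primary comparison, in a trial of 112 patients whose SAP expects a substantial share of primary data to be missing. SAP 9 also plans formal between-arm tests of baseline variables but no response to an imbalance. Covariates chosen after seeing those tests would be data-driven, so any adjustment needs to be fixed beforehand.

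**Working it through.** **Inputs**

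- SD: the pilot value in "comparable post-CA patients was 8.9" percentage points (SAP 5, same figure in protocol 6.9.1).
- Target: "to show a 40% reduction in the extent of cerebral ischemia" (SAP 5). No control mean is given.
- Error rates: "with a power of 80% at a two-sided alpha level of 0.05" (SAP 5).
- Size: "56 patients would be necessary in each study group" (SAP 5), so 112 in total.
- R², the share of outcome variance that the added covariates explain beyond rhythm: not in the documents. Assumed values are 0 to 0.30. The SD of 8.9 is taken as the residual SD of the planned model (also an assumption, since rhythm may already explain part of it).

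**Step 1: the plan's own figure.** Without a control mean, 56 per arm cannot be reproduced forwards. Solving backwards:

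δ = SD × (z0.975 + z0.80) × √(2/n) = 8.9 × (1.960 + 0.842) × √(2/56) = 4.71 points.

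As a 40% reduction, this implies a control mean of 4.71/0.40 = 11.8%. The noncentral t gives 4.75 points, or 4.75/8.9 = 0.534 SD.

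**Step 2: adjustment with complete data.** The residual SD becomes 8.9 × √(1 − R²), and

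power = Φ(2.802/√(1 − R²) − 1.960).

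At R² = 0.20 this is Φ(2.802/0.894 − 1.960) = Φ(1.17) = 88%. The 95% CI half-width is 1.96 × residual SD × √(2/56). The equivalent unadjusted N is 112/(1 − R²).

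| Assumed R² | Residual SD | Power | CI half-width | CI narrower by | Equivalent N |
|---|---|---|---|---|---|
| 0 | 8.90 | 80% | 3.30 | – | 112 |
| 0.05 | 8.67 | 82% | 3.21 | 3% | 118 |
| 0.10 | 8.44 | 84% | 3.13 | 5% | 124 |
| 0.20 | 7.96 | 88% | 2.95 | 11% | 140 |
| 0.30 | 7.45 | 92% | 2.76 | 16% | 160 |

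Charging 3 further degrees of freedom in a noncentral t calculation does not change the rounded power figures.

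**Step 3: missing data and multiple imputation.** SAP 10.1 expects missing values but gives no rate, so 15% and 30% are assumptions. The simulation used 1,500 trials per scenario, 112 patients, a difference of 4.71 and an SD of 8.9. One baseline covariate explained R² of the outcome and also influenced missingness. There were 25 imputations per trial (the SAP plans 100), pooled by Rubin's rules. The covariate was always in the imputation model, and only the analysis model differed.

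| Missing | R² | Two-factor ANOVA | Adjusted model | Gain (points) |
|---|---|---|---|---|
| 15% | 0 | 72.1% | 71.3% | −0.8 |
| 15% | 0.10 | 71.9% | 75.4% | 3.5 |
| 15% | 0.20 | 73.6% | 81.1% | 7.5 |
| 15% | 0.30 | 73.0% | 84.3% | 11.3 |
| 30% | 0 | 60.1% | 60.0% | −0.1 |
| 30% | 0.10 | 61.5% | 64.9% | 3.4 |
| 30% | 0.20 | 65.1% | 71.3% | 6.2 |
| 30% | 0.30 | 65.1% | 75.7% | 10.6 |

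With complete data and R² = 0, the same simulation gave 79.1% for the ANOVA and 78.2% for the adjusted model. The Monte Carlo standard error of a single figure near 65% is √(0.65 × 0.35/1500) = 1.2 points.

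**Step 4: reading.** Having the covariate in the imputation model helps to fill in missing values. It does not take the variance that the covariate explains out of the ANOVA error term, so it does not replace adjustment in the analysis model.

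**The case against.** The strongest reply is that nothing here is an error. The two-factor ANOVA adjusts for the protocol's stratification factor, as SAP 7.3 intends, agrees with the protocol, and gives a valid test. That stands.

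Four further objections also carry weight:

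- **Size.** A reader might infer that the plan is known to give up as much as 12 points of power. The documents do not support that. They report no association between these covariates and the ADC measure, and an R² near zero fits them equally well. The 80-to-92% levels also assume complete data, which SAP 10.1 does not expect, and apply to the untransformed scale, whereas SAP 7.5 allows a log transformation.
- **The sponsor's view.** A reader might infer that the sponsor already regards these variables as predictors of the endpoint. Imputation variables can be chosen because they predict missingness, and the SAP 7.8 subgroups are exploratory. Gender is in both lists and is not proposed here, while time to ROSC is proposed but is absent from SAP 7.4. The covariate set is therefore a judgement.
- **Timing.** The SAP postdates inclusion of all patients, and the primary model is fixed in protocol 6.9.3. Changing it is more than a one-line SAP edit.
- **Completeness.** The documents do not say how often time to ROSC is missing. Protocol 6.4 records whether the arrest was witnessed, so the start time may be uncertain for some patients.

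These points limit the claim but do not remove it. At R² = 0 almost nothing is lost, and at modest R² the gain persists under multiple imputation.

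**Conclusion.** The point holds as an inexpensive improvement in efficiency. A reader might infer that the two-factor ANOVA is biased or unsound. It is not: randomisation protects the comparison, and the test is valid without the extra terms.

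The gain depends wholly on an R² that the documents do not give. For R² of 5 to 30% and complete data it is about 2 to 12 points of power. With 30% missing it is about 3 to 11 points for R² of 10 to 30%. The direction is secure if the covariates predict the outcome beyond rhythm; the size is an assumption. Adjustment removes chance imbalance only in the covariates modelled, and only in the form modelled.

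**What to change.** Before unblinding, prespecify in SAP 10.1 a primary model with treatment, shockable rhythm, age (continuous), time to ROSC (continuous, functional form fixed in advance) and bystander CPR. Fit it in each imputed data set and pool as already planned. Include every analysis covariate in the SAP 7.4 imputation model, which means adding time to ROSC. Do not adjust for the post-randomisation variables used for imputation (NSE, day-1 EEG, death within 7 days). Report the two-factor ANOVA as a supporting analysis.

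Cost: no new data and 3 degrees of freedom. Missing times to ROSC, whose number is not stated, must be imputed. Because this changes the primary model named in protocol 6.9.3, the reason, the date and the blinded state of the data must be recorded under protocol 6.10. If it cannot be shown that the change was made while blinded, the adjusted model should be only a supporting analysis.

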### 10.2 Secondary Endpoints

The statistical analysis of all secondary endpoints will be performed for the FAS and PPS.

### 10.2.1 CPC 3-5 at Discharge

Since patients who died in-hospital will have a CPC score of 5, it is expected that the number of patients with missing data will be negligible.

Therefore, the %patients with CPC 3-5 at discharge will be analysed using a Cochran-Mantel-Haenszel test with shockable rhythm as stratification factor.

The effect of randomised group will be estimated by the stratified odds ratio between the two groups and presented along with its 95% confidence interval.

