4. INTRODUCTION

4.1. The clinical problem

There is absolutely no doubt that sudden cardiac death is a major problem in Belgium in terms of numbers of patients, medical impact and socio-economic impact. Each day, approximately 30 adults suffer from an unexpected out-of-hospital cardiac arrest in Belgium, a number exceeding the incidence of breast or prostate cancer with an estimated 25 new patients per day in Belgium. In addition, many cardiac arrest patients are young (mean age in our hospital 60±12 years, 56% of patients younger than 65 years) with a large economic potential for society. In the community, the occurrence of sudden death often takes center stage through highly mediatised cases of cardiac arrest in young sportsmen with or without a previously undiscovered cardiac anomaly. Apart from the traumatic experience of these dramatic sudden events, only 40% of patients that reach the hospital with spontaneous circulation survive without major neurological impairment or care dependency. An additional 5-10% of the cohort survives with major neurological impairment including a permanent vegetative state. These sobering outcome data and the large economic burden for society (estimated cost of a nursing home facility for these patients approximately 30-50000 €/year) mandate novel treatment strategies that could improve prognosis after cardiac arrest.

Apart from temperature management to avoid fever, no single in hospital randomized controlled intervention trial has improved outcome of these patients. In this way, there is absolutely no doubt that a positive result of the Neuroprotect post-CA trial would be a clear added value for this vulnerable and highly under-investigated patient group.

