## 1 Purpose

This document provides a detailed description of the statistical analyses prescribed in the final protocol (version 4, dated 20Jan2017), that will be performed for the evaluation of the primary safety, secondary efficacy, clinical and safety endpoints of the NEUROPROTECT study.

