### **7.3 Statistical Comparisons between Groups**

Since randomization was stratified by the presence of shockable rhythm, all comparisons between groups should account for this stratification.

So, an ANOVA using factors for randomized group and shockable rhythm will be used rather than a two-sample t-test for the comparison of continuous and normally distributed variables. Continuous variables showing serious deviations from normality will be compared using a Van Elteren test. This test will also be used for the comparison of ordinal data.

For binary and categorical data, a Cochran-Mantel-Haenszel test will be used.

For primary and secondary variables, the effect of treatment will be estimated by an appropriate statistic and presented together with its associated 95% confidence interval.

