### 10.2.2 CPC 3-5 at 180 Days

The %patients with CPC 3-5 at Day 180 will be analysed using the same methodology as used for the analysis of the CPC scores at discharge (see section 10.2.1) whereby all patients who did not have CPC scores due to death are given a score of 5.

A sensitivity analysis will be performed whereby all patients who did not die and do not have CPC data will be given a score of 5.

### 10.2.3 SF-36 Questionnaire at Day 180

Of main interest is the total score obtained from the SF-36 questionnaire. In addition, the subscales will be analysed using the same methodology.

It should be kept in mind that a considerable proportion of patients will have died prior to Day 180 and that therefore, the SF-36 results in these patients are not defined. A comparison of the scores in the survivors will yield biased estimates of the treatment effect, since the element of randomisation is lost in such comparison if survival depends on the assigned treatment group.

Therefore, the effect of randomised group will be evaluated by the "survivor average causal effect" (SACE), defined as the effect of randomised treatment on the outcome among the subgroup of patients that would have survived under either treatment arm. The SACE will be calculated as explained by Hayden et al by weighing the result of each survivor by the estimated survival probability in the other group. The confidence interval will be obtained by bootstrapping (500 samples).

The estimated survival probabilities will be obtained from a logistic regression using survival as dependent variable and the baseline covariates given in Section 7.4 as independent variables.

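### The SAP gives only stratified odds ratios for the binary secondary endpoints where the protocol prescribes risk ratios; for CPC 3-5 the two measures differ widely

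*SAP*

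**What the plan says.** Protocol 6.9.3 fixes both the test and the effect measure for binary secondary endpoints. On the test: "Binary secondary endpoints will be analyzed by means of a stratified Chi-squared test". On the measure: "Treatment differences will be expressed as risk ratios and presented along with their corresponding 95% confidence intervals".

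SAP 10.2.1 analyses CPC 3-5 at ICU discharge with a Cochran-Mantel-Haenszel (CMH) test stratified by shockable rhythm, and then says: "The effect of randomised group will be estimated by the stratified odds ratio between the two groups". SAP 10.2.2 says that CPC 3-5 at 180 days "will be analysed using the same methodology as used for the analysis of the CPC scores at discharge", so it inherits the odds ratio. SAP 10.2.11 uses the same odds-ratio sentence for tracheostomy. These are all the binary secondary efficacy endpoints, and none has a risk ratio or risk difference planned.

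The SAP's general rule in 7.3 is only that, for primary and secondary variables, "the effect of treatment will be estimated by an appropriate statistic and presented together with its associated 95% confidence interval". SAP section 1 defines the document's role: "This document provides a detailed description of the statistical analyses prescribed in the final protocol", namely version 4 of 20 January 2017. Protocol 6.10 requires any change to the planned analyses after study start to be documented with its date, its reason, who was responsible and what data were then available.

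On how common a poor outcome is, protocol 4.1 says that "only 40% of patients that reach the hospital with spontaneous circulation survive without major neurological impairment or care dependency". Protocol 4.4 repeats the 40% figure.

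**The concern.** The protocol names a measure, and the SAP, which presents itself as describing the protocol's analyses, uses a different one without comment. For a rare event this would be close to a formality, because odds ratio and risk ratio nearly coincide. CPC 3-5 is not rare: the protocol's own figure makes it the majority outcome. The number reported for neurological outcome would then sit on a scale other than the prespecified one. A reader who takes the odds ratio as a relative risk would see a larger effect than the data show, whether it is a benefit or a harm.

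**Working it through.** The documents give no assumed CPC or tracheostomy effect, so there is no planned figure to reproduce. The only design calculation (56 per group) concerns the MRI endpoint. It is used here only as a group size in step 4.

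**Inputs**
- Control risk of CPC 3-5: 1 − 0.40 = 0.60, from protocol 4.1 and 4.4. The range 0.50 to 0.70 is an assumption.
- Risk ratios: assumptions, since the documents state none for CPC.
- Tracheostomy rate: not given. Rates of 5%, 10% and 20% are assumptions.

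**Formula.** With control risk pc and treated risk pt = RR × pc,

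OR = [pt/(1 − pt)] / [pc/(1 − pc)] = RR × (1 − pc)/(1 − pt).

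**1. CPC 3-5 at pc = 0.60**

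| Assumed RR | pt | OR | Reduction in risk | Reduction in odds |
|---|---|---|---|---|
| 0.90 | 0.54 | 0.90 × 0.40/0.46 = 0.78 | 10% | 22% |
| 0.75 | 0.45 | 0.75 × 0.40/0.55 = 0.55 | 25% | 45% |
| 0.60 | 0.36 | 0.60 × 0.40/0.64 = 0.375 | 40% | 62% |

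Over these rows the log odds ratio is about 1.9 to 2.3 times the log risk ratio.

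**2. Sensitivity to the control rate, RR = 0.75**
- pc = 0.50: pt = 0.375, OR = 0.75 × 0.50/0.625 = 0.60.
- pc = 0.70: pt = 0.525, OR = 0.75 × 0.30/0.475 = 0.47.

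**3. Does stratification remove the gap?** Assume 70% shockable with 50% poor outcome and 30% non-shockable with 83.3%. Overall this is 0.70 × 0.50 + 0.30 × 0.833 = 0.60. Apply RR 0.75 in both strata with 56 per group:
- Shockable (39.2 per group): 14.7 treated and 19.6 control events. Odds-ratio terms: 14.7 × 19.6/78.4 = 3.675 and 24.5 × 19.6/78.4 = 6.125.
- Non-shockable (16.8 per group): 10.5 treated and 14 control events. Terms: 10.5 × 2.8/33.6 = 0.875 and 6.3 × 14/33.6 = 2.625.
- Mantel-Haenszel OR = (3.675 + 0.875)/(6.125 + 2.625) = 4.55/8.75 = 0.52. The Mantel-Haenszel RR is 0.75.

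The gap therefore remains after stratification.

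**4. Effect on inference.** Take 25/56 against 34/56 as an unstratified illustration with Wald intervals:
- RR 0.74 (95% CI 0.51 to 1.05), p = 0.094.
- OR 0.52 (95% CI 0.25 to 1.11), p = 0.090.

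The conclusion is the same. The planned p-value comes from the CMH test, which does not depend on which measure is reported beside it.

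**5. Tracheostomy, RR = 0.75.** At assumed control rates of 5%, 10% and 20% the OR is 0.74, 0.73 and 0.71. The gap is small unless the event is common, and the documents do not say that it is.

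**The case against.** The strongest reply is that an odds ratio is a valid measure, that it will be labelled as one, and that protocol 6.9.3 leaves the full methods to the SAP. SAP 7.2 also requires frequencies and percentages by group, so any reader can work out the crude risks and their ratio. The odds ratio has an advantage too: it simply inverts when the outcome is relabelled. At 60% against 45% poor outcome, the risk ratio is 0.75 for CPC 3-5 but 0.55/0.40 = 1.375 for CPC 1-2.

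Much of this stands. The odds ratio is not wrong in itself, and any distortion depends on its being misread. But leaving detail to the SAP does not explain replacing a measure that the protocol names, and a general reference to an appropriate statistic gives no reason. Group percentages do not supply a stratified risk ratio with its confidence interval.

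A reader might infer more than the documents support:
- **That the switch was data-driven.** The SAP refers to the blinded review of 5 March 2018 as past, so its text was finalised after all patients were included. But SAP 3.4 keeps the statistician blinded until after database lock, and a record under protocol 6.10 may exist outside the SAP. What is established is only that the SAP gives no reason.
- **That significance or type I error is affected.** The CMH test is a stratified chi-squared test of the kind the protocol asks for.
- **That tracheostomy results would be inflated.** No rate is given to support this.
- **That this is the trial's headline result.** The primary endpoint is the MRI measure, and the documents do not rank the secondary endpoints.

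The 40% figure also describes patients reaching hospital with spontaneous circulation, without a stated time point. The trial's eligibility criteria could move its own rate either way, hence the range in the working.

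**Conclusion.** The inconsistency between protocol and SAP is explicit and covers all three binary secondary efficacy endpoints. For CPC 3-5 it changes the reported estimate materially: an assumed risk ratio of 0.75 would be reported as an odds ratio of 0.55 at a 60% control rate. Two assumptions carry this size: that the trial's control rate is near the protocol's background figure, and the chosen risk ratio. The direction needs neither, because whenever there is an effect the odds ratio lies further from 1 than the risk ratio. For tracheostomy only the inconsistency is shown. The point concerns how an effect is expressed, not whether it is detected. It should be corrected, but it does not threaten the validity of the tests.

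**What to change.** In SAP 10.2.1, 10.2.2 and 10.2.11, keep the CMH test and report the Mantel-Haenszel risk ratio stratified by shockable rhythm with its 95% CI, as in protocol 6.9.3. The odds ratio may follow as supportive. State that CPC 3-5 (or tracheostomy) is the event and standard care the reference, because the risk ratio depends on that choice. Use the same measure in the sensitivity analyses of 10.2.2 and 10.2.11.

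If the odds ratio is to remain the main measure, document the change and its reason as protocol 6.10 requires, and still give the stratified risk ratio alongside.

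The cost is negligible: no new data, patients or tests, and the stratified risk ratio comes from the same stratified tables. The one downside is presentational: the stated effect will look less extreme.
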